10.1.3.3. Time to Progression

Time to progression is calculated as the time from study enrollment, defined as the IVRS enrollment date, until the first recorded disease progression on the IMWG assessment of response CRF or LTFU CRF, whichever occurs first, or death due to PD (refer to PFS for complete event details).

Censoring of subjects not experiencing an event are similar to PFS outlined in Table 1 with the following exceptions:

- If a subject is still on therapy and therefore has no LTFU CRFs, then censor at time of last response assessment, otherwise,
- If the subject did not have a disease progression during therapy but has entered into long term follow-up and still no disease progression is indicated, then censor at the time of the last completed LTFU CRF.

10.1.3.4. Overall Survival

Overall survival is calculated as the time from study enrollment, defined as the IVRS enrollment date, until death due to any cause. Subjects who do not have death data at the time of study end/analysis will be censored at the time they were last known to be alive.

11. STATISTICAL ANALYSIS OF SAFETY ENDPOINTS

All safety analyses will be performed on the safety population.

11.1.1. Adverse Events

Adverse Events will be coded according to the Medical Dictionary for Regulatory Activities (MedDRA) version 15 or higher. The severity of AEs will be graded according to the NCI CTCAE version 4.0. Summaries will be by system organ class and preferred term.

Treatment-emergent AEs (TEAEs) are defined as any AE occurring or worsening on or after the first treatment of the IP and within 28 days after the last dose. If a subject experiences the same preferred term multiple times then the event will be counted only once and by the greatest severity.

All TEAEs, TEAEs leading to IP discontinuation, TEAEs leading to dose reduction/interruption, TEAEs related to the IP, serious TEAEs, serious TEAEs related to study medication, and serious TEAEs leading to study medication discontinuation will be summarized by system organ class and preferred term. Summary of TEAEs with NCI-CTCAE grade 3 or 4 and with NCI-CTCAE grade 5 will also be provided. Summary of TEAEs by dosing cycle will also be provided. Where necessary, adverse events will be categorized by using specified MedDRA hierarchy terms (i.e., SOC, HLGT, HLT, and PT), and/or by Standardized MedDRA Queries (SMQs); the number and percentage of subjects with adverse events alone and/or with concurrent events, medical history, medications, laboratory values, etc., may be tabulated, and where possible, may be organized or displayed by specific parameters (e.g., time to occurrence, other demographics, exposure/duration/cycle, therapy period(s), etc.) . Where necessary, and as the data allow, incidence rates will be calculated, summarized and displayed.

If a subject experiences the same preferred term multiple times then the subject will be counted only once by the greatest severity of that term when presented in tabulations.

An AE listing will be presented separately for individual subjects.

Adverse Events of Special Interest

Analysis of AEs of special interest will be presented with tabulations for: TEAEs of interest, NCI-CTCAE grade 3 or 4 TEAEs of interest, TEAEs of interest related to study medication, serious TEAEs of interest and TEAEs of interest leading to study medication discontinuation. The following AE of interest categories and preferred terms include but are not limited to:

- neutropenia
- febrile neutropenia
- infection
- thrombocytopenia
- hemorrhage and bleeding
- neuropathy
- DVT (deep vein thrombosis)
- PE (pulmonary embolism)

- SPM (second primary malignancies)
- muscular weakness
- glucose intolerance
- mood alteration
- cataract
- cardiovascular events/dysrhythmia
- fluid retention/edema
- hematopoietic cytopenias

In addition the following tables will be presented to further investigate the corresponding AEs of interest:

- treatment emergent neutropenia and febrile neutropenia by GCSF usage on study
- treatment emergent arterial thrombotic events with and without prophylaxis medications (where prophylaxis medication is defined as low-dose aspirin, low molecular weight heparin, or other equivalent antithrombotic or anticoagulant within one week of prior to onset of event)
- treatment emergent venous thrombotic events with and without prophylaxis medications (where prophylaxis medication is defined as low-dose aspirin, low molecular weight heparin, or other equivalent antithrombotic or anticoagulant within one week of prior to onset of event)
- treatment emergent DVT with and without concurrent PE (where concurrent PE is defined as PE onset within +/- two weeks of onset of DVT, and before resolution of DVT)
- treatment emergent neuropathy by baseline neuropathy status
- time to onset of neuropathy from enrollment
- time to improvement/resolution of neuropathy from enrollment
- time to worsening/new incidence of neuropathy from enrollment
- neuropathy still ongoing at treatment discontinuation
- treatment emergent grade 3 or higher infections and infestations and concurrent neutropenia (where concurrent grade 3 or 4 neutropenia is defined as grade 3 or 4 neutropenia onset within +/- two weeks of onset of infection and infestation, and before resolution of infection and infestation)
- treatment emergent grade 3 or higher neutropenia and concurrent infections and infestations (where concurrent grade 3 or 4 infections and infestations is defined as grade 3 or 4 infections and infestations onset within +/- two weeks of onset of neutropenia, and before resolution of neutropenia)
- treatment emergent (grade 3 or higher) thrombocytopenia with concurrent haemorrhage and bleeding (where concurrent bleeding is defined as bleeding onset within +/- two weeks of onset of thrombocytopenia, and before resolution of thrombocytopenia)

- treatment emergent (grade 3 or higher) haemorrhage and bleeding with concurrent thrombocytopenia (where concurrent grade 4 thrombocytopenia is defined as grade 4 thrombocytopenia onset within +/- two weeks of onset of bleeding, and before resolution of bleeding)
- summary and incidence of second primary malignancy (SPM)

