14.3.1.3.2	Summary of Dose Reductions by Cycle: Safety Population
14.3.1.4.1	Summary of Dose Interruptions: Safety Population
14.3.1.4.2	Summary of Dose Interruptions by Cycle: Safety Population
14.3.2.1	Summary of Treatment Emergent Adverse Events: Safety Population
14.3.2.2.1	Treatment Emergent Adverse Events: Safety Population
14.3.2.2.2	Treatment Emergent Adverse Events with CTCAE Grade 2 or Higher Infections: Safety Population
14.3.2.3	Treatment Emergent Adverse Events with CTCAE Grades 3 or 4: Safety Population
14.3.2.4.1	Treatment Emergent Adverse Events Related to Any Study Drug: Safety Population
14.3.2.4.2	Treatment Emergent Adverse Events Related to Pomalidomide: Safety Population
14.3.2.4.3	Treatment Emergent Adverse Events Related to Low-Dose Dexamethasone: Safety Population
14.3.2.5.1	Treatment Emergent CTCAE Grade 3 or 4 Adverse Events Related to Any Study Drug: Safety Population

14.3.2.5.2	Treatment Emergent CTCAE Grade 3 or 4 Adverse Events Related to Pomalidomide: Safety Population
14.3.2.5.3	Treatment Emergent CTCAE Grade 3 or 4 Adverse Events Related to Low-Dose Dexamethasone: Safety Population
14.3.2.6.1	Cause of Death During Treatment Period: Safety Population
14.3.2.6.2	Cause of Death During First 60 Days of Treatment: Safety Population
14.3.2.6.3	Cause of Death After 28 Days of End of Treatment: Safety Population
14.3.2.6.4	Cause of Death: Safety Population
14.3.2.6.5	Cause of Death During Screening Period: Non-enrolled Subjects
14.3.2.7	Treatment Emergent Grade 5 Adverse Events: Safety Population
14.3.2.8	Treatment Emergent Serious Adverse Events: Safety Population
14.3.2.9.1	Treatment Emergent Serious Adverse Events Related to Any Study Drug: Safety Population
14.3.2.9.2	Treatment Emergent Serious Adverse Events Related to Pomalidomide: Safety Population
14.3.2.9.3	Treatment Emergent Serious Adverse Events Related to Low-Dose Dexamethasone: Safety Population
14.3.2.9.4	Treatment Emergent Serious Adverse Events Leading to Discontinuation of Any Study Drug: Safety Population
14.3.2.9.5	Treatment Emergent Serious Adverse Events Leading to Discontinuation of Pomalidomide: Safety Population
14.3.2.9.6	Treatment Emergent Serious Adverse Events Leading to Discontinuation of Low-Dose Dexamethasone: Safety Population
14.3.2.10.1	Treatment Emergent Adverse Events Leading to Discontinuation of Any Study Drug: Safety Population
14.3.2.10.2	Treatment Emergent Adverse Events Leading to Discontinuation of Pomalidomide: Safety Population

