16.2.6.10	Individual CC-4047 Plasma Concentrations (ng/mL): Pharmacokinetic Population
16.2.7.1.1	Treatment Emergent Adverse Events
16.2.7.1.2	Pre-treatment and Post-treatment Adverse Events
16.2.7.1.3	Treatment Emergent Adverse Events Leading to Pomalidomide Discontinuation
16.2.7.1.4	Treatment Emergent Adverse Events Leading to Low-Dose Dexamethasone Discontinuation
16.2.7.1.5	Treatment Emergent CTCAE Grade 3 or 4 Adverse Events
16.2.7.1.6	Grade 5 Treatment Emergent Adverse Events
16.2.7.1.7	Treatment Emergent CTCAE Grade 2 or Higher Infections and Concomitant Antibiotic Medication
16.2.7.2	Serious Adverse Events
16.2.7.3.1	Deaths During Treatment Period
16.2.7.3.2	Deaths During First 60 Days of Treatment
16.2.7.3.3	Deaths After 28 Days of End of Treatment
16.2.7.3.4	Deaths for Enrolled Subjects
16.2.7.3.5	Deaths During Screening Period: Non-enrolled Subjects

16.2.7.4	Adverse Events of Clinical Interest
16.2.8.1.1	Local Laboratory - Chemistry
16.2.8.1.2	Local Laboratory - Hematology
16.2.8.1.3	Local Laboratory – Urinalysis
16.2.8.1.4	Local Laboratory - Renal Function Assessment
16.2.8.1.5	Local Laboratory – Immunoglobulins
16.2.8.2	Local Serum Free Light Chain Assessment
16.2.8.3	Vital Signs
16.2.8.4	ECG
16.2.8.5	ECOG Performance Status
16.2.8.6	Healthcare Resource Utilisation
16.2.8.7	Second Primary Malignancies
16.2.8.8	Second Primary Malignancies Procedures
16.2.8.9	Second Primary Malignancy Regimen Therapy
16.2.8.10	Second Primary Malignancy Radiation Therapy

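### Read literally, the table of grade 3 or higher neutropenia with concurrent infection leaves out fatal (grade 5) infections

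*SAP*

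**What the plan says.** Among the additional tables for adverse events of interest, SAP section 11.1.1 describes a mirror pair linking neutropenia and infection.

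- **Neutropenia as index (Table 14.3.2.16.14.1).** The label is "treatment emergent grade 3 or higher neutropenia and concurrent infections and infestations". The parenthesis that follows gives the only definition of the concurrent event: "where concurrent grade 3 or 4 infections and infestations is defined as grade 3 or 4 infections and infestations onset within" two weeks either side of neutropenia onset, and before the neutropenia resolves.
- **Infection as index (Table 14.3.2.16.14.2).** The label is "treatment emergent grade 3 or higher infections and infestations and concurrent neutropenia". The concurrent neutropenia is limited to grade 3 or 4, but the infection has no upper grade limit.

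The same section shows how the SAP uses its grade terms: "Summary of TEAEs with NCI-CTCAE grade 3 or 4 and with NCI-CTCAE grade 5 will also be provided". It also sets a counting rule for repeated preferred terms, under which "the subject will be counted only once by the greatest severity of that term when presented in tabulations".

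Appendix B keeps the same separation. Table 14.3.2.3 is "Treatment Emergent Adverse Events with CTCAE Grades 3 or 4: Safety Population" and Table 14.3.2.7 is "Treatment Emergent Grade 5 Adverse Events: Safety Population". Listing 16.2.7.1.5 is "Treatment Emergent CTCAE Grade 3 or 4 Adverse Events", and grade 5 events have their own Listing 16.2.7.1.6.

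**The concern.** The neutropenia-indexed bullet uses two grade phrases that differ in this SAP. The index event is grade 3 or higher, while the concurrent infection is grade 3 or 4. Because the SAP consistently treats grade 5 as a separate category, a programmer who follows the text would filter the infections to grades 3 and 4 and drop the fatal ones.

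Safety is the primary objective (section 2), and neutropenia and infection are both listed as adverse events of interest. This is the only listed table that answers the question: among subjects with severe neutropenia, how many had a severe infection close in time? A reader would expect the answer to include the infections that killed the subject.

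**Working it through.** The point rests on definitions, so the check sets the passages side by side. The SAP gives no figure to reproduce.

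**1. Infection grades admitted by each table (section 11.1.1)**

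| Table | Index event | Infection grades counted |
|---|---|---|
| 14.3.2.16.14.1 | Neutropenia, grade 3 or higher | 3, 4 |
| 14.3.2.16.14.2 | Infection, grade 3 or higher | 3, 4, 5 |

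The difference is grade 5. As a further comparison, the bullet on grade 3 or higher thrombocytopenia with concurrent bleeding puts no grade limit on the bleeding, so fatal bleeding is not excluded there.

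**2. Whether grade 3 or 4 could be shorthand for severe.** It is kept apart from grade 5 in three places: the summaries in section 11.1.1, Tables 14.3.2.3 and 14.3.2.7, and Listings 16.2.7.1.5 and 16.2.7.1.6. The bullet itself also uses the inclusive phrase for the neutropenia. The shorthand reading has no support in the document.

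**3. Whether another table fills the gap.** Three table titles in Appendix B name neutropenia: 14.3.2.16.11, 14.3.2.16.14.1 and 14.3.2.16.14.2. Two use it as the index (.11 and .14.1). One of these two shows infections (.14.1). Under the literal definition, none of these counts a grade 5 infection.

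**4. Worked example (invented days).** Grade 4 neutropenia starts on day 20 and does not resolve. Pneumonia starts on day 25. The gap is 25 − 20 = 5 days, within 14 and before resolution.

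| Pneumonia | In .14.1? | In .14.2? |
|---|---|---|
| Grade 4 | Yes | Yes |
| Grade 5 | No | Yes |
| Grade 3 on day 25, grade 5 on day 30, same preferred term | No, if greatest severity is taken before the grade filter | Yes |

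The SAP does not fix the order of the two steps in the last row, so that result depends on programming.

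**5. Whether the missing cases can be read from the mirror table.** Only in part. Table .14.1 requires infection onset before the neutropenia resolves. Table .14.2 requires neutropenia onset before the infection resolves. A neutropenia that resolved before the infection began can count in .14.2 but not in .14.1. The fatal cases in .14.2 may therefore include some that do not belong in .14.1.

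**6. Size.** Let f be the share of subjects with a fatal infection among those with a concurrent grade 3 to 5 infection. The undercount is at most f, because a subject with a fatal infection who also had a separate qualifying grade 3 or 4 infection would still be counted. Per 100 such subjects, the table shows at least 100 × (1 − f). The values of f are assumed and do not come from the SAP.

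| f | Shown, at least |
|---|---|
| 5% | 95 |
| 10% | 90 |
| 20% | 80 |

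**The case against.** The strongest counter-argument is that the parenthesis defines a row, not the rule for entering the table. The term it defines carries a grade, while the bullet's label and the Appendix B title put no grade on the infection. A neighbouring bullet has the same form: its label mentions concurrent thrombocytopenia without a grade, and the definition is for grade 4. On that reading the table might show infections of any grade, with grade 3 or 4 as one line. This is possible, but the SAP defines no any-grade row, and the line for severe infections would still omit grade 5.

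Second, reporting grade 3 or 4 separately from grade 5 is the SAP's own convention. That is true, but elsewhere the convention comes with a matching grade 5 output. Here there is none.

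Third, little information is lost. This largely stands. Table 14.3.2.16.14.2 captures fatal infections with grade 3 or 4 neutropenia. Fatal infections also appear in Tables 14.3.2.7 and 14.3.2.16.10, the cause-of-death tables and the listings, and section 11.1.1 allows further tabulation of concurrent events. However, the SAP does not say that .14.2 will show grade 5 as its own row, and none of the other table titles links the infection to neutropenia.

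Fourth, the greatest-severity point depends on a programming order that the SAP does not state, and the range for f is not taken from the document. Both are correct. Neither is needed for the main point.

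**Conclusion.** The point holds. As written, the definition excludes grade 5 infections from the only neutropenia-indexed table of concurrent infection, and it is inconsistent with its mirror bullet. If the parenthesis describes a row, that row has the same gap.

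The consequence is limited to one descriptive table. The adverse event incidence tables that carry the primary endpoint are not affected, and no formal hypothesis testing is planned (section 4.1.4). The number of subjects concerned cannot be derived from the SAP. The 5% to 20% range illustrates the possible undercount and is not an estimate for this trial. It is still worth correcting, because the omitted outcome is the worst one in a trial whose primary objective is safety.

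**What to change.** In section 11.1.1, define the concurrent infection for Table 14.3.2.16.14.1 as grade 3 or higher (3, 4 or 5), to match the infection-indexed bullet. If the parenthesis is meant as a row of the table, say so and make that row grade 3 or higher.

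The cost is one changed definition and one grade filter in one table. No new data are needed.

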11.1.2. Second Primary Malignancies

Second primary malignancies include any regardless of the causal relationship to the IP (POM with or without DEX).

11.1.3. Deaths

Deaths during treatment period (i.e. after the first treatment of the IP and within 28 days after the last actual dose of study drug received) will be tabulated for the safety population. Deaths during the first 60 days of treatment and after 28 days after the last actual dose of study drug received will also be tabulated.

11.1.4. Clinical Laboratory Evaluations

Clinical laboratory values will be graded according to NCI CTC version 4.0 for applicable tests. Baseline grade and worst severity grade (both high and low, as appropriate) observed during the treatment period for selected laboratory results will be summarized. Furthermore, the shift from baseline to the worst grade observed during the treatment period for selected laboratory results will also be presented. Normal ranges will be used to determine the categories if High, Low and Normal for lab tests with no assigned severity grade. Listings of clinical laboratory data with abnormal flags will be provided by subject and test.

11.1.5. Vital Signs

For vital signs, a shift during treatment from baseline to worse for below-, within-, and above-normal range categories will be displayed in cross-tabulations. Normal ranges are defined as follows:

- Systolic blood pressure (BP) → Normal (90 – 119 mmHg, inclusive)
- Diastolic BP → Normal (60 – 79 mmHg, inclusive)
- Body Temperature → Normal (36.1 – 37.8 degrees centigrade, inclusive)

Descriptive statistics (N, Mean, Standard Deviation, Median, Minimum and Maximum) of observed and change from baseline values will be presented.

11.1.6. Electrocardiogram

The overall ECG interpretation will be summarized by presenting the number and percentage of subjects with “Normal” “Abnormal, not clinically significant” and “Abnormal, clinically significant”. Shift from baseline to worst during study, as well as shift from baseline by cycle in the overall ECG interpretation will be displayed in cross-tabulations tabulations.

Other ECG measurements such as QTc will be tabulated with summary statistics (N, Mean, Standard Deviation, Median, Minimum and Maximum) of observed and change from baseline values presented.

11.1.7. ECOG Performance Status

Shift from baseline to worst during study, shift from baseline to best during study, as well as shift from baseline by cycle in ECOG performance status will be displayed in cross-tabulations.

12. PHARMACOKINETIC ANALYSIS

All PK and PD related table, figures and listings will be provided in a separate delivery document.

12.1. Software for Analysis

The software to be used in the pharmacokinetic data analysis and data presentation includes:

- SAS Version 9.1.3 or higher (SAS Institute, Inc., Cary, NC)
- SigmaPlot Version 10.0 or higher (Systat Software, Inc., Point Richmond, CA)

12.2. Analysis population

As a data cut-off date of May 4th 2015, all subjects who receive POM and have PK data will be included. If any subjects are found to be noncompliant with respect to dosing, or encounter other circumstances that could affect the evaluation of PK, a decision will be made on a case-by-case basis as to their inclusion in the PK analysis. Data excluded from PK analysis and/or statistical analysis will be included in the data listings, but not in the summaries.

12.3. Pharmacokinetic Analysis

12.3.1. Data handling

Pre-dose concentrations that are below the limit of quantification (BLQ) or missing will be assigned a number value of zero.

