12.3.2. Statistical Analysis

POM plasma concentrations will be listed and summarized by cycle using descriptive statistics (N, mean, SD, coefficient of variation [CV%], geometric mean, geometric CV%, median, Min, and Max). Box-Whisker plot of POM plasma concentrations will be generated.

[REDACTED]

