Appendix B: Tables Graphs and Listings

Tables Section 14.

Table Number	Table Title
14.1.1	Analysis Populations
14.1.2.1	Subject Disposition – Treatment Phase: All Populations
14.1.2.2	Subject Disposition – Long-term Follow-up Phase: All Populations
14.1.3	Summary of Reasons for Screen Failure: Screen Failure Subjects
14.1.4	Subjects Enrolled by Study Site: Intention to Treat Population
14.1.5	Summary of Protocol Violations: Intention to Treat Population
14.1.6	Summary Demographic and Baseline Characteristics: All Populations
14.1.7	Baseline Disease Characteristics: All Populations
14.1.8	Medical History: All Populations
14.1.9	Prior Cancer History: All Populations
14.1.10	Prior Medications: All Populations
14.1.11	Prior Therapies: All Populations
14.1.12	Summary of Prior Anti-myeloma Therapies by Drug Class: All Populations
14.1.13	Summary of Last Prior Anti-myeloma Therapies by Drug Class: All Populations
14.1.14	Refractory Status to Selected Prior Anti-myeloma Therapies: All Populations
14.1.15	Summary of Prior Anti-myeloma Treatment Lines and Regimens: All Populations
14.1.16	Evidence of Progression Status to Last Anti-myeloma Therapies: All Populations
14.1.17	Prior Cancer Surgeries for this Disease: All Populations
[REDACTED]	[REDACTED]
14.1.19	Prophylactic Medications During the Treatment Period: Safety Population
[REDACTED]	[REDACTED]

14.1.21	Summary of Prior Venous Thromboembolic Events: All Populations
14.1.22	Summary of Cytogenetic Data: All Populations
14.2.1.1	Summary of Overall Response and Response Rates: All Populations
14.2.1.2	Overall Survival Follow-up: All Populations
14.2.2	Summary of Time to Response (TTR): All Populations
14.2.3	Summary of Duration of Response (DoR): All Populations
14.2.4	Summary of Time to Progression (TTP): All Population
14.2.5.1	Summary of Progression Free-Survival (PFS): According to EMA Guidelines: All Populations
14.2.5.2	Summary of Progression Free-Survival (PFS): According to FDA Guidelines: All Populations
14.2.6	Summary of Overall Survival (OS): All Populations
14.2.7	Summary of Subsequent Anti-myeloma Therapy: Intention to Treat Population
14.2.8	Summary of CC-4047 Plasma Concentrations (ng/mL) by Cycle: Pharmacokinetic Population
14.3.1.1	Summary of Treatment Duration: Safety Population
14.3.1.2.1	Summary of Dose Information: Safety Population
14.3.1.2.2	Summary of Dose Information by Cycle: Safety Population
14.3.1.3.1	Summary of Dose Reductions: Safety Population

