14.2.3.1	Kaplan-Meier Curve for Progression Free Survival Based on EMA Guidelines: Intention to Treat Population
14.2.3.2	Kaplan-Meier Curve for Progression Free Survival Based on FDA Guidelines: Intention to Treat Population
14.2.4	Kaplan-Meier Curve for Overall Survival: Intention to Treat Population
14.2.5	Waterfall Plot of Maximum Change in M-Protein from Baseline: Intention to Treat Population
14.2.6	Box-Whisker Plot of the Plasma Concentrations by Cycle
14.3.1	Time to Onset of Hematologic and Solid Tumor Second Primary Malignancies: Safety Population

Listings Section 16.

Listing Number	Title of Listing
16.2.1	Discontinued Subjects
16.2.2	Protocol Violations
16.2.3	Participation in Previous Celgene Studies
16.2.4.1	Demographic and Baseline Characteristics
16.2.4.2	Medical History
16.2.4.3	Disease Diagnosis
16.2.4.4	Prior Anti-myeloma Therapy
16.2.4.5	Prior Radiation Therapy for Myeloma
16.2.4.6	Prior Cancer Surgery for Myeloma
16.2.4.7.1	Prior Stem Cell Transplant for Myeloma
16.2.4.7.2	Prior Therapies for Stem Cell Transplant Conditioning
16.2.4.8	Prior Bisphosphonate Therapy for Bone Lesions
16.2.4.9.1	Evidence of Most Recent Disease Progression
16.2.4.9.2	Evidence of Disease Progression with Last Lenalidomide-containing Regimen
16.2.4.9.3	Evidence of Disease Progression with Last Bortezomib-containing Regimen
16.2.4.10	Prior Medications
██████	████████████████████
██████	██
16.2.4.13	Cytogenetic Assessment
16.2.4.14	Skeletal Survey
16.2.4.15	Bone Marrow Assessment
16.2.4.16	Venous Thromboembolic Event
16.2.4.17	Pregnancy Status and Test Results
16.2.4.18	Subject Eligibility
16.2.4.19	Prior Cancer History

16.2.4.20	Prior Cancer History II – Diagnostic Exams for Cancer Within 6 months Prior to Screening
16.2.4.21	Prior Procedures for Cancer Not Under Study
16.2.4.22	Prior Radiation Treatment for Cancers not Under Study
16.2.4.23	Prior Regimen Treatment for Cancers not Under Study
16.2.5	Study Drug Record: Pomalidomide and Low-Dose Dexamethasone
16.2.6.1	Investigator Assessment of Response (IMWG Criteria)
16.2.6.2	Variables for Determination of Myeloma Response
16.2.6.3	Clinical Plasmacytomas Assessment
16.2.6.4	Radiological Plasmacytomas Assessment
16.2.6.5.1	Subsequent Anti-myeloma Therapy
16.2.6.5.2	Subsequent Stem Cell Transplant for Myeloma
16.2.6.5.3	Subsequent Therapies for Stem Cell Transplant Conditioning
16.2.6.6	Follow-up Therapies
16.2.6.7	Long-term Progression Follow-up
16.2.6.8	Survival Follow-up

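### SAP 12.3.1 sets missing pre-dose pomalidomide concentrations to zero at any cycle, so samples never obtained enter the by-cycle PK summaries as measured zeros

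*SAP*

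**What the plan says.** Section 12.3.1 of the SAP is a single sentence, and it is the only visible rule for handling concentration values: "Pre-dose concentrations that are below the limit of quantification (BLQ) or missing will be assigned a number value of zero". It mentions neither the first dose nor any cycle or day.

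Section 12.3.2 then plans that "POM plasma concentrations will be listed and summarized by cycle using descriptive statistics". These include N, mean, SD and also "coefficient of variation [CV%], geometric mean, geometric CV%, median, Min, and Max". Appendix B lists the outputs: Table 14.2.8, "Summary of CC-4047 Plasma Concentrations (ng/mL) by Cycle: Pharmacokinetic Population", and Figure 14.2.6, "Box-Whisker Plot of the Plasma Concentrations by Cycle".

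Section 12.2 defines who is included: "all subjects who receive POM and have PK data will be included". It allows case-by-case decisions on subjects with dosing non-compliance or other circumstances affecting the PK evaluation, and adds: "Data excluded from PK analysis and/or statistical analysis will be included in the data listings, but not in the summaries".

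**The concern.** A concentration below the limit of quantification and a sample that was never obtained are different kinds of record. The first is an observation, and zero is a common stand-in for it. The second carries no information about drug level. For a subject already on treatment there is no reason to take the absent value as zero.

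Because the rule assigns a number, the absent sample becomes an ordinary record in the by-cycle summary. It counts in N and enters the mean, SD, CV%, median and minimum. A reader would normally take N in Table 14.2.8 as the number of measured samples, and under this rule it is not. The box plot is affected in the same way.

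The rule also differs from the plan's general approach. For categorical data, section 4 keeps missing records out of the percentage denominator. That provision does not govern continuous data, but it shows that elsewhere the plan does not count a missing record as an observed one.

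**Working it through.** **Step 1: follow the value through the text.** The SAP states no figure on this point, so there is nothing to reproduce.

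- Section 12.3.1: a missing pre-dose value becomes 0, at whatever time point it was due.
- Section 12.2: subjects with no PK data are out. The rule therefore acts only on absent samples of subjects who have other PK data.
- Section 12.2 again: exclusions are case by case, for reasons affecting the PK evaluation. Excluded data are listed and not summarised. Nothing there says that a zero assigned to an absent sample is such an exclusion.
- Section 12.3.2, Table 14.2.8 and Figure 14.2.6: the values are summarised by cycle.

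So an absent pre-dose sample appears as 0 in the summary of its cycle.

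**Step 2: size, by illustration.** The SAP does not show the missing share, the CV, the sampling days or the mix of pre- and post-dose samples. Assumptions: pre-dose samples only, missing at random, log-normal concentrations with coefficient of variation c of 40%, 60% or 80%, and a fraction f set to zero.

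- Change in N relative to samples obtained: 1/(1−f) − 1
- Relative change in mean: −f
- New CV: √[(1+c²)/(1−f) − 1]
- New median / old median: exp{σ·z[(0.5−f)/(1−f)]}, where σ = √ln(1+c²) and z is the standard normal quantile

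Worked case, f = 0.10 and c = 0.40:

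- N: 1/0.90 − 1 = +11.1%
- Mean: −10%
- CV: √(1.16/0.90 − 1) = 0.537
- Median: (0.5−0.1)/0.9 = 0.444 and σ = √ln 1.16 = 0.385, giving −5.2%

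| Missing | N | Mean | Median (CV 40 / 60 / 80%) | CV 40 / 60 / 80% becomes |
|---|---|---|---|---|
| 1% | +1.0% | −1% | −0.5 / −0.7 / −0.9% | 41 / 61 / 81% |
| 2% | +2.0% | −2% | −1.0 / −1.4 / −1.8% | 43 / 62 / 82% |
| 5% | +5.3% | −5% | −2.5 / −3.6 / −4.5% | 47 / 66 / 85% |
| 10% | +11.1% | −10% | −5.2 / −7.5 / −9.4% | 54 / 71 / 91% |
| 20% | +25% | −20% | −11.6 / −16.2 / −20.1% | 67 / 84 / 102% |

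A simulation of 2,000,000 values at CV 60% agrees. With f = 0.02 it gives mean −2.0%, median −1.4% and CV 62%; with f = 0.10, mean −10.0%, median −7.4% and CV 71%.

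**Step 3: two cases where the effect is smaller.**

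*Pre- and post-dose samples pooled within a cycle.* Assume that half the records are post-dose (p = 0.5 pre-dose), that none of those are missing, and that their mean is 3 times the pre-dose mean. The change in mean is [p(1−f) + 3(1−p)]/[p + 3(1−p)] − 1. At f = 0.10 this is (0.45 + 1.5)/2 − 1 = −2.5%. For 1, 2, 5, 10 and 20% missing, the mean falls by 0.25, 0.5, 1.25, 2.5 and 5.0%. N rises by 1/(1−pf) − 1, which is 0.5, 1.0, 2.6, 5.3 and 11.1%.

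*True pre-dose values already near zero.* Section 8.6 computes planned intensity from 21 dosing days in 28, so a Day 1 sample in a later cycle could follow dose-free days. In the simulation (geometric mean 10, CV 60%), with 75% of true values already zero, the absolute fall in the mean is 0.06 at f = 0.02 and 0.29 at f = 0.10. With none at zero it is 0.23 and 1.16. When most values are already zero the median is zero either way and does not move. What mainly remains is the inflated N.

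**Step 4: geometric statistics.** Any zero, whether from a BLQ or a missing sample, makes the geometric mean 0 (for 10, 12, 15 and 0 it is 0) or undefined on the log scale. The geometric CV% then cannot be computed unless a convention is set.

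**The case against.** The strongest objection is that the harm depends on a sampling schedule the SAP does not show. If the only pre-dose sample is the one before the first dose, zero is the expected value and little bias follows. A by-cycle table makes pre-dose sampling in later cycles plausible but does not prove it. This stands as a limit on the size of the bias. It does not rescue the rule: under any schedule, N includes samples that were never obtained, and the sentence contains no first-dose restriction.

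A second objection is that text after section 12.3.2 is redacted, and section 12 says "All PK and PD related table, figures and listings will be provided in a separate delivery document". A qualification could sit in either place. That is a fair reason to treat the geometric-mean issue only as a point to confirm. It carries less weight for the main point, because the rule in 12.3.1 is visible, complete and unqualified. A later text that reversed it would leave the SAP contradicting itself.

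Third, section 12.2 allows case-by-case exclusions and keeps excluded data out of summaries. That is a discretionary route and does not expressly cover imputed zeros.

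Fourth, no input to the size calculation comes from the trial, and the realistic effect may be very small. This is accepted: at 1 to 5% missing in the pooled case, the mean moves by 0.25 to 1.25%.

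**Conclusion.** The rule is wrong as written. It gives an unobserved pre-dose sample the value of a measured one, at any cycle, and passes it into the by-cycle summaries. N is overstated whenever such a sample is missing. The mean is lowered and CV% raised where true pre-dose concentrations are above zero; the median is lowered too, unless most values are already zero.

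The size in this trial cannot be derived from the SAP. The figures above rest on assumed missing shares, CVs, log-normality and random missingness, and they run from negligible to material. The consequence is confined to descriptive PK output, namely Table 14.2.8 and Figure 14.2.6. No effect is claimed on population PK, exposure-response modelling, or the safety and efficacy results. The correction should still be made, because the rule is explicit and the remedy is almost free.

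**What to change.** Delete the words *or missing* from section 12.3.1. A missing concentration then stays missing at every time point and is left out of N and of all summaries. If the sponsor prefers to keep zero for an absent sample where no drug can yet be present, the sentence should say that this applies only to the sample before the first dose; N would then still count any such absent sample.

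Separately, confirm that the redacted text or the separate PK delivery document says how zeros, including BLQ zeros, enter the geometric mean and geometric CV%. Add one sentence only if neither does.

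The cost is two words and a smaller but true N in some PK summaries, plus at most one sentence on zeros in the geometric statistics.
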